5.7. Contraindications

Subcutaneous administration of Furosemide Injection Solution is not intended for use is emergency situations such as acute decompensated heart failure or in patients with pulmonary edema.

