John Hopkins Heart Failure Bridge Clinic (HFBC)

CLINICAL RESEARCH PROTOCOL

Prospective, Randomized, Parallel-Group Pilot Study Comparing IV Furosemide to Subcutaneous Furosemide in Decompensated Heart Failure Patients

Protocol Number: Protocol Date: 2015 - 1 05 August 2015

| | SYNOPSIS |
|----------------------------|---|
| PROTOCOL TITLE | Prospective, Randomized, Parallel-Group Pilot Study Comparing IV Furosemide to Subcutaneous Furosemide in Decompensated Heart Failure Patients |
| PROTOCOL NUMBER | |
| SPONSOR | Johns Hopkins Heart Failure Bridge Clinic (HFBC) |
| INVESTIGATIONAL PRODUCT | Furosemide Injection Solution, (SCP-101) 8 mg/mL manufactured by Cook Pharmica for scPharmaceuticals, Inc. (test treatment) and Furosemide Injection, USP 10 mg/mL (reference treatment) |
| STUDY OBJECTIVES | The objectives of this study are: |
| | Primary objective: To determine the clinical efficacy of subcutaneously administered Furosemide Injection Solution (SCP -101) versus intravenous administration of Furosemide Injection, USP in adult patients at the HFBC presenting with decompensated heart failure. |
| | Secondary objective: To determine the adverse effects and patient satisfaction with subcutaneously administered Furosemide Injection solution (SCP-101) versus intravenous administration of furosemide in adult patients at the HFBC presenting with decompensated heart failure. |

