1.1. Rationale for the Current Study

The research hypothesis is that subcutaneously administered furosemide will be an effective alternative to IV furosemide for hemodynamically stable chronic heart failure patients presenting with volume overload in the ambulatory setting. The significance of this research is finding a potential intervention that could help decrease heart failure hospitalizations and improve the quality of life for patients with chronic heart failure. In addition, we can decrease the costs associated with heart failure.

There is very little experience with subcutaneous administration of furosemide EP/USP (current form of commercially available furosemide injection solution). There are a few studies that show the delivery of subcutaneous furosemide by electric infusion pump in terminally ill patients is effective for weight loss and symptom improvement (1,2). A group in Spain was successfully able to resolve 41 episodes of decompensated heart failure in 24 elderly patients using continuous subcutaneous furosemide administered by elastomeric infusion pumps (2). They found that the elastomeric infusion pumps provided safe outpatient treatment without the need for daily monitoring. In addition, it helped prevent hospital admissions and decreased costs due to the low price of the devices. It was also a good alternative for patients with venipuncture failure and the inability to transition from intravenous to oral diuretics.

Furosemide USP has a pH of 8.3 -9.0 and may cause irritation and discomfort upon administration. A novel buffered formulation with a physiologic pH (7.4) is currently under development in support of a NDA submission later in 2015. The product is to be marketed with a wearable patch pump for a slow 5-hour administration to optimize 8-hour diuresis.

scPharmaceuticals, Inc. (Lexington, MA), the developer of the novel furosemide formulation and its drug delivery device, provided the following information. The pivotal clinical study with the buffered furosemide solution (Furosemide Injection Solution (SCP-101)) started in Q2 of 2015 in support of the NDA. This study is conducted in the United States in stable HF patients under IND 118,919.

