3. INVESTIGATIONAL PLAN

3.1. Overall Study Design and Plan

This clinical trial is a prospective, randomized, parallel-group pilot study comparing the intravenous administration of Furosemide Injection, USP, to subcutaneous administration of a buffered furosemide formulation – Furosemide Injection Solution (SCP-101), in patients presenting to the Johns Hopkins Hospital Heart Failure Bridge Clinic with decompensated heart failure. Patients presenting to the HFBC will be assessed to determine whether they need IV diuretics. If they need it, they will be screened for eligibility. If they are eligible, written informed consent will be provided. Patients will then be randomized to receive Furosemide Injection, USP intravenously, or SCP-101 delivered subcutaneously. The IV patients will get the usual care of the Heart Failure Bridge Clinic, which includes having an IV placed and delivery of a one-time dose of IV furosemide with the dose determined by the providers (maximum dose 160mg IV). The subcutaneous patients will receive 80mg of Furosemide Injection Solution, 8 mg/mL, administered subcutaneously over 5 hours (30mg in first hour and 12.5mg/hour for 4 hours).

Administration will take place with the BBraun Perfusor® Space Infusion Pump System and a standard commercial infusion set. Both groups of patients will be observed for 6 hours to assess diuresis. The goal will be to enroll a total of 40 patients, 20 in the IV furosemide group, and another 20 in the subcutaneous furosemide group. Vital signs and urine output

will be monitored closely for 6 hours. Patients will be asked to fill out a survey about their symptom improvement (Kansas City Cardiomyopathy questionnaire) and overall satisfaction related to the treatment experience. They will also be monitored for side effects including ototoxicity and discomfort at the access site (burning, itching, and pain). Electrolytes and renal function will be checked once after the patients receive diuretic therapy. Study participants will be on fluid restriction during the study, with no more than 100 ml of fluid consumed during the 6 hours.

Study Drug:

- *Furosemide Injection, USP:* Furosemide Injection, Solution, single dose determined by Investigator (maximum dose 160mg) administered intravenously by IV bolus over approximately 2 minutes (reference treatment).

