4. SELECTION OF STUDY POPULATION

4.1. Inclusion Criteria

Female and male subjects are eligible for inclusion only if all of the following criteria are met:

Inclusion Criteria (low risk, intermediate risk):

- An Institutional Review Board (IRB) approved informed consent is signed and dated prior to any study-related activities
- Male and female subjects ≥ 18 years of age
- History of at least 3 months treated heart failure (NYHA class II/III/IV), or recent hospitalization for heart failure; presenting to HFBC with decompensated heart failure symptoms including elevated jugular venous pressure, dyspnea and peripheral edema where the decision is made to give IV diuretics
- Able to participate in the study in the opinion of the investigator
- Has the ability to understand the requirements of the study and is willing to comply with all study procedures

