4.2. Exclusion Criteria

A Subject is not eligible for inclusion if any of the following criteria apply

- Presenting with symptoms where it is anticipated that there is a high chance of hospitalization such as ischemia, uncontrolled arrhythmia, infection, hemodynamic instability (elevated or low blood pressure), respiratory compromise, or electrolyte abnormalities (>25% increase in creatinine from baseline, potassium, hyponatremia)
- On experimental medication or currently participating in a cardiovascular research study.
- Presence or need for urinary catheterization, urinary tract abnormality or disorder interfering with urination
- Any surgical or medical condition which in the opinion of the investigator may interfere with participation in the study or which may affect the outcome of the study
- Inability to comply with study requirements

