6.1.4. Physical Examinations

A cardiopulmonary examination will be conducted and consist of assessments of the following: heart sounds, murmur, chest sounds, pedal edema and peripheral pulses.

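### Section 5.7 says the subcutaneous product is not intended for emergency decompensation or pulmonary edema, but no eligibility criterion carries that limit

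*Combined protocol and SAP*

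**What the plan says.** Section 5.7, headed Contraindications, is a single sentence. It says that subcutaneous administration of the buffered furosemide solution is "not intended for use is emergency situations such as acute decompensated heart failure or in patients with pulmonary edema" (I read the stray verb near the start as a slip for the preposition in).

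The population is described elsewhere:

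- The title gives it as "Comparing IV Furosemide to Subcutaneous Furosemide in Decompensated Heart Failure Patients", and section 3.1 randomizes to either route "in patients presenting to the Johns Hopkins Hospital Heart Failure Bridge Clinic with decompensated heart failure".
- Section 4.1 admits NYHA class II to IV patients "presenting to HFBC with decompensated heart failure symptoms including elevated jugular venous pressure, dyspnea and peripheral edema", once the decision to give IV diuretics has been made.
- Section 4.2 excludes presentations thought likely to end in hospitalization. Its examples include "hemodynamic instability (elevated or low blood pressure), respiratory compromise". A separate item excludes any condition that the investigator thinks may interfere with participation or affect the outcome.
- Section 1.1 states the hypothesis for "hemodynamically stable chronic heart failure patients presenting with volume overload in the ambulatory setting".

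The synopsis repeats both eligibility lists. Section 5.5 makes the study open label, and section 8.2 calls for an intention-to-treat analysis.

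**The concern.** Section 5.7 limits who should receive the test product, but it sits outside the criteria that decide who is randomized. Staff who screen from section 4 could allocate a patient to a product that the same protocol says is not intended for that patient. That is a safety question first.

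It is also a question for the comparison. The limit attaches to the subcutaneous product and not to IV furosemide. If it is noticed only once the allocation is known, any resulting non-treatment or withdrawal falls on one arm. With 20 patients planned per arm, a very small number of such cases is visible in the result.

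**Working it through.** The plan states no figure on this point, so the check is mainly a comparison of texts.

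**1. Where the terms occur.** Pulmonary edema appears only in section 5.7. No item in 4.1, 4.2 or the synopsis names it or points to 5.7. Acute decompensated heart failure is not defined, and no criterion separates it from the decompensation that is enrolled.

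**2. What 5.7 covers.** The sentence has two parts. The first concerns emergency situations and gives acute decompensated heart failure as an example. The second, introduced by its own preposition, concerns patients with pulmonary edema and is not tied to an emergency.

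**3. Could a patient pass section 4 and still fall under 5.7?** Take a dyspneic patient with pulmonary edema who is not expected to be admitted.

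| Provision | What it tests | Does it settle 5.7? |
|---|---|---|
| 4.1, symptoms | Raised venous pressure, dyspnea, peripheral edema, IV diuretic decision | No; such a patient can qualify |
| 4.2, likely hospitalization | Forecast of admission; respiratory compromise is one example | Only if admission is anticipated, a test that 5.7 does not use |
| 4.2, hemodynamic instability | Glossed as high or low blood pressure | No; it does not address the lungs |
| 4.1 and 4.2, investigator opinion | Ability to take part; interfering conditions | Possibly, but discretionary and without mention of 5.7 |
| 6.1.4, screening examination | "heart sounds, murmur, chest sounds, pedal edema and peripheral pulses" | No eligibility rule uses the finding |

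So the answer is yes, in a limited set of cases.

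**4. Timing.** The Time and Events Schedule places randomization in the screening phase, ahead of the pre-dose and dosing columns. There is therefore an interval in which staff know the allocation and have not yet dosed. Section 4.4 allows the investigator to end participation for safety reasons.

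**5. Effect on the analysis.** Let k of the 20 subcutaneous patients not receive the product because of 5.7, and let f = k/20. Write m_SC and m_IV for mean 6-hour outcomes on each route, and m_other for the mean under whatever the k patients receive instead. As a simplification, assume these means are the same for affected and unaffected patients. If all outcomes are collected, the intention-to-treat contrast is

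(1 − f)(m_SC − m_IV) + f(m_other − m_IV).

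If those k patients were given usual IV treatment instead (an assumption; the protocol does not say), the second term is zero and the contrast keeps the fraction 1 − f of its size:

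- k = 1: 1 − 1/20 = 0.95
- k = 2: 1 − 2/20 = 0.90

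These values of k are illustrative. Under that assumption the arms look more alike than the routes are. This is not a conservative error when section 1.1 hypothesizes that the subcutaneous route is an effective alternative.

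If the k patients leave without a 6-hour urine collection, they are missing from one arm while similar patients remain in the other. The result is then biased by an amount that depends on how their outcomes differ from the rest. The documents give nothing from which to size that.

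**The case against.** The best defence is that the protocol is plainly written for patients who are not emergencies. Section 1 contrasts those who should be hospitalized with those who are volume overloaded but stable, and section 1.1 frames the hypothesis for the latter. The inclusion list is labelled low and intermediate risk, and the synopsis labels the exclusions high risk. The hospitalization exclusion is open-ended and lists respiratory compromise. A condition that the protocol itself puts under Contraindications is an obvious prompt for the investigator-opinion exclusion. The study has one site, and study staff give every dose.

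Much of this stands, and it defeats two stronger readings that a reader might infer:

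- *That 5.7 bars the whole enrolled population, and so all 20 subcutaneous patients.* The sentence limits acute decompensated heart failure to emergency situations, and the trial aims at stable ambulatory patients. The text does not support a conflict for every patient.
- *That non-treatment in one arm destroys the comparability created by randomization.* Under intention-to-treat, patients stay in their assigned arm whether or not they are treated. Non-treatment mainly dilutes the contrast; bias arises only if outcomes are lost.

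The defence does not close the pulmonary edema gap. Hemodynamic stability is stated in the background and rationale, not as an inclusion criterion. Forecast hospitalization is a different test from the one in 5.7, and the discretionary items do not direct anyone to it.

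**Conclusion.** The point holds in a limited form. The pulmonary edema part is the firmer one: a contraindication is stated in 5.7 and no eligibility criterion matches it. The part on acute decompensation is an undefined boundary rather than a flat contradiction, because existing provisions probably catch most emergency presentations.

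The mismatch in the text is certain, but how often it would matter is unknown. The documents give no fraction of clinic patients with pulmonary edema who would not be expected to be admitted, and I do not supply one. All that can be said is that each affected patient is 5% of the planned subcutaneous arm. The validity argument also assumes that someone acts on 5.7 after allocation. If nobody does, the issue is one of safety and protocol consistency only. Sample size and significance level are unaffected.

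**What to change.** Before enrolment, reconcile section 5.7 with sections 4.1 and 4.2 and the synopsis so that they describe the same population, and state which patients 5.7 refers to. Whether the eligibility criteria or 5.7 should change, and in what words, is for the clinical team. Whatever condition is retained should be an eligibility item, checked and recorded before the allocation envelope is opened, so that it applies equally to both arms.

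The cost is a wording change and, under section 9.1.2, IRB approval of the amendment. The cardiopulmonary examination is already scheduled at screening. The protocol does not say that it can identify pulmonary edema, so the clinical team must confirm whether it is sufficient. A few patients may become ineligible. At about 15 IV diuretic treatments a month, the planned 3 to 4 months supply 3 × 15 = 45 to 4 × 15 = 60 treatments for 40 enrolments, so the margin for extra screen failures is modest and the timeline may lengthen slightly.

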5.8. Treatment Compliance

All study medication will be administered by study personnel and all information regarding study drug administration will be documented.

5.9. Study Drug Accountability

Study drug will be administered in accordance with the procedures of this protocol. Only authorized site personnel may supply or administer study drug and only subjects enrolled in the study may receive study drug, in accordance with applicable regulatory requirements.

6. STUDY PROCEDURES

6.1. Study Measurements and Assessments

6.1.1. Assessment of Efficacy

Diuresis:

Urine will be collected from start of treatment through 6 hours post initiation of treatment. Individual voids will be measured and then pooled over the 6 hour time period, and the volume of the pool will be recorded. Time of voids and volume of each void will be recorded.

Natriuresis:

Participants will not be given any fluid by mouth during the 6-hour observation period, except when required for taking oral medication, in which case fluid intake will be limited to 100mL over the 6 hour period.

A 5mL aliquot of the first void, and a 5 mL aliquot of the total 6 hour pool will be obtained by the study staff for determination of sodium.

Symptomatic Improvement

Symptom scoring using the Kansas City Cardiomyopathy questionnaire will be performed prior to drug administration and at the end of the 6 hour observation period. A treatment satisfaction survey will be conducted at 6 hours.

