1. INTRODUCTION

The prevalence of chronic heart failure is increasing, and it is the most common diagnosis in hospital patients age 65 years and older. Despite advances in the treatment of chronic heart failure, in-hospital mortality and readmission are high. Heart failure costs the US about 32 billion per year, and a large percentage of the costs are due to hospitalizations. The Heart Failure Society of America guidelines for the management of decompensated heart failure offer recommendations for clinical circumstances that should prompt hospital admission. Most clinicians would agree that patients with decompensated heart failure presenting with hypotension, worsening renal function and altered mental status should be hospitalized. However, there is a subset of patients presenting with dyspnea and edema due to volume overload that necessitate rapid symptom improvement but are hemodynamically stable. Oral diuretics would likely be ineffective but admission for IV diuretics seems excessive.

The Johns Hopkins Heart Failure Bridge Clinic (HFBC) was designed as a clinic to reduce heart failure hospital admissions. Patients with chronic heart failure are primarily seen either in the early post discharge period or if they are referred for an infusion of IV diuretic. The HFBC sees about 160 patients each month and administers on average 15 infusions of Intravenous (IV) diuretics. The average visit duration is 220 minutes, with mean IV furosemide dose 100mg resulting in average urine output 1460 ± 730 ml, and weight loss of 2.3 ± 1.8 kg.

The HFBC has been successful at preventing hospital admissions by treating patients with IV diuretics. However, it requires patients to come to the clinic for treatment and close monitoring. Subcutaneous diuretics present a potential alternative to IV diuretics and offer patients an opportunity to receive treatment outside of the hospital setting. Very few studies have evaluated the efficacy and safety of subcutaneous furosemide in chronic heart failure patients presenting with symptoms of volume overload.

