3.1.1. Endpoints

Primary Endpoints:

- 1) Total volume of voids over a 6-hour period
- 2) Total natriuresis over a 6-hour period

Secondary endpoints:

- 1) Volume of voids between 0-2 hours, 2-4 hours and 4-6 hours post initiation of treatment.
- 2) Heart Failure Symptom Scoring/Symptom Improvement- (Kansas City Cardiomyopathy questionnaire)
- 3) Overall Satisfaction with Treatment- (Treatment Satisfaction Survey)

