6.1.3. Clinical Laboratory Tests

All routine samples will be analyzed by a licensed clinical laboratory. The clinical laboratory tests are as follows:

- **Blood Clinical Chemistry**: blood urea nitrogen (BUN), creatinine, sodium, potassium, calcium, chloride, magnesium and bicarbonate.
- BNP/NTproBNP
- Urinalysis: A 5 ml aliquot from the first void post start of treatment and a 5 ml aliquot from the pooled urine voids over the 6 hour observation period will be analyzed for sodium.

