8.2. Statistical Analysis Plan

A full statistical analysis plan will be developed. All data will be analyzed as intention-totreat. Continuous variables will be presented as mean \pm standard deviation and will be compared using the Students *t*-test (2-tailed), unpaired. Differences between treatment groups for the categorical variables will be analyzed using the chi-square test. For the purposes of this study, *P* values $\leq .05$ will be considered significant.

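### No void is requested just before dosing or at 2, 4 and 6 hours, so the 2-hour volumes depend partly on when patients void and both 6-hour totals can miss or gain bladder urine

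*Combined protocol and SAP*

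**What the plan says.** Section 3.1.1 names two primary endpoints, the volume voided and the sodium excreted over 6 hours. Its first secondary endpoint is "Volume of voids between 0-2 hours, 2-4 hours and 4-6 hours post initiation of treatment".

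The collection procedure is in Section 6.1.1: "Urine will be collected from start of treatment through 6 hours post initiation of treatment". Voids are measured one by one and then pooled, and "Time of voids and volume of each void will be recorded". The schedules (Synopsis Table 1 and Appendix 1) mark the row for collecting and measuring voids at start of dosing, during dosing and at 6 hours, but not at pre-dose.

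On urine sodium, Section 6.1.1 calls for "A 5mL aliquot of the first void" and an aliquot of the 6-hour pool. Section 6.1.3 says "A 5 ml aliquot from the first void post start of treatment". Both schedules mark urine sodium at pre-dose and at 6 hours.

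Section 8.2 gives no rule for allotting voids to intervals, but says "A full statistical analysis plan will be developed".

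**The concern.** A void empties urine formed since the previous void. Unless patients void at the cut-points, urine is credited to the window in which it is passed, not the one in which it was formed. If flow changes over the 6 hours, the recorded intervals blur the time course, and each patient's void timing adds noise. The time course is what these windows would be expected to show, since one arm receives a bolus over about 2 minutes and the other a 5-hour infusion.

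The same gap touches both ends of the pool behind the two primary endpoints. Urine still in the bladder at 6 hours is not counted. Urine formed before dosing is counted if the bladder was not emptied first.

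**Working it through.** **Step 1. The text at each time point**

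| Time | Section 6.1.1 | Both schedules |
|---|---|---|
| Before dosing | No emptying void | Urine sodium marked; void collection not marked |
| 2 h, 4 h | No void requested | Void collection marked under dosing, no clock times |
| 6 h | Collection ends; no void requested | Void collection marked |

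There is no figure in the plan to reproduce. The rest is illustration.

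**Step 2. Inputs**

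- From Section 1: mean urine output 1460 mL, SD 730 mL, for clinic visits with IV diuretic.
- Assumed: formation split 60/25/15% over the three windows, that is 876/365/219 mL, or 438, 182.5 and 109.5 mL/h.
- Assumed: the void pattern and the bladder content at dosing. The documents give neither.

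**Step 3. Voids at fixed intervals, empty bladder at dosing**

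With voids every T hours at random phase, the time a since the last void is uniform on 0 to T, with mean T/2 (0.5 h for T = 1, 1.0 h for T = 2). Mean recorded volumes:

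- 0-2 h: 876 − 438 × T/2 = 657 mL (T = 1) or 438 mL (T = 2), a shortfall of 219 or 438 mL.
- 2-4 h: 365 + (438 − 182.5) × T/2 = 493 or 621 mL.
- 4-6 h: 219 + (182.5 − 109.5) × T/2 = 256 or 292 mL.
- SD of the 0-2 h volume from timing alone: 438 × T/√12 = 126 or 253 mL.

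Under constant flow, the 2-4 h and 4-6 h means are unchanged.

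**Step 4. Voids triggered by volume**

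Same flow profile, each void triggered at an assumed 200-400 mL (simulation):

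- Empty bladder at dosing: about 711/374/218 mL. The 0-2 h shortfall is 876 − 711 = 165 mL, and about 157 mL is unvoided at 6 h.
- With 50-150 mL already in the bladder: about 824/364/215 mL. The 0-2 h shortfall is 876 − 824 = 52 mL, because counted pre-dose urine offsets part of the loss.

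**Step 5. What prorating by recorded void times recovers (Step 3 pattern)**

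The mean error at a cut-point is (drop in flow) × T/6.

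- At 2 h: 255.5/6 = 43 mL or 255.5 × 2/6 = 85 mL. The 0-2 h volume becomes 833 or 791 of 876 mL.
- At 4 h: 73/6 = 12 mL or 73 × 2/6 = 24 mL. With no 6 h void, the 4-6 h volume is 219 + 12 − 55 = 176 mL or 219 + 24 − 110 = 134 mL (rounded) of 219 mL.

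**Step 6. The 6-hour totals**

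- Unvoided at 6 h, fixed intervals: 109.5 × 0.5 to 1.0 = 55-110 mL. Constant flow (1460/6 = 243.3 mL/h): 122-243 mL.
- Counted from before dosing: assumed 50-150 mL.
- Net: 50 − 243 = −193 mL to 150 − 55 = +95 mL, or −13% to +7% of 1460 mL.
- SD of the total: √(730² + 31.6²)/730 = 1.001 to √(730² + 140.5²)/730 = 1.018 from closing timing, where 31.6 = 109.5/√12 and 140.5 = 243.3 × 2/√12. Adding an opening SD of 50-150 mL (assumed) gives 1.003 to 1.039.

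**Step 7. Between arms**

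A simulation used an assumed front-loaded profile for IV, an assumed sustained profile for subcutaneous, and mean void thresholds of 200, 300 and 400 mL.

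| | IV | Subcutaneous |
|---|---|---|
| 0-2 h shortfall (mL) | 907−806 = 101; 891−735 = 156; 898−697 = 201 | 430−332 = 98; 425−278 = 147; 423−228 = 195 |
| Unvoided at 6 h (mL) | 98; 150; 201 | 100; 151; 201 |

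Here the losses nearly cancel in the difference between arms. With fixed-interval voiding they need not: each 100 mL/h difference in flow at 6 h would shift the difference in totals by 100 × 0.5 to 1.0 = 50-100 mL.

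**Step 8. Urine sodium**

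A pre-dose sample (schedules) and a sample from a void after treatment starts (Section 6.1.3) cannot be the same sample. Section 6.1.1 fits the latter, since its collection begins with treatment. The pooled 6-hour sample is the same in all places.

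**The case against.** The endpoints are worded as volumes of voids, and every void is timed and measured, so as written they are fully observed. That stands as wording. But the stated purpose of the 6-hour observation is to assess diuresis, and a window defined by voids serves it only as far as it reflects urine formed in that window.

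Recorded times permit prorating, and the SAP is still to be written. This also stands for the 0-2 hour window, most of which prorating repairs. No section says it will be done, however, and no SAP can recover urine never voided by 6 hours.

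A reader might infer that the 6-hour pool is simply left open. The schedules do not support so flat a statement: they mark void collection at 6 hours, and staff may take that as a closing void. The mark is ambiguous and does not request a void.

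A reader might also infer from the 438/621/292 mL result that the peak window would be misidentified. That depends on voiding every 2 hours whatever the flow, which at 438 mL/h means single voids of up to 876 mL. With voids of 200-400 mL, the first window stays the largest on average.

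Finally, the 730 mL SD comes from visits of a different length ("The average visit duration is 220 minutes"). If it was measured from voids, it already contains some timing noise, so the SD increases in Step 6 may double-count.

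**Conclusion.** The gap in the procedure is clear from the text. Its size is not, because the documents give no void frequency, hourly flow or bladder content.

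Under the assumed front-loaded profile, the 0-2 hour volume is understated by about 165 mL with voids of 200-400 mL from an empty bladder, by about 50 mL if 50-150 mL of pre-dose urine is present, and by 219-438 mL with voids every 1-2 hours. About 55-160 mL is unvoided at 6 hours, and up to 243 mL under constant flow and 2-hourly voids.

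The main effect is on one secondary endpoint of a 40-patient pilot. For the two primary totals, the losses and gains partly offset and the SD rises by at most about 4%. It would be tempting to call the primary comparison biased. The documents do not support that: whether the arms differ in urine left at 6 hours, and in which direction, depends on flow and voiding patterns that they do not give.

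The urine sodium conflict is real but minor. It does not undermine total natriuresis, taken here as pooled sodium concentration times pooled volume (the protocol does not write the formula), and no listed endpoint uses the first sample.

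This is an inexpensive improvement worth making before enrollment, since unvoided urine cannot be reconstructed later.

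**What to change.** 1. In Section 6.1.1 and both schedules, ask each patient to empty the bladder just before dosing, and keep this void out of the pool.
2. In the same places, request voids at 2, 4 and 6 hours, with the 6-hour void closing the pool. Record on the CRF when a patient cannot void.
3. In the SAP, prorate any void that straddles a cut-point by the recorded void times.
4. As a separate small item, reconcile the pre-dose urine sodium mark in Synopsis Table 1 and Appendix 1 with Sections 6.1.1 and 6.1.3. The emptying void could supply a pre-dose sample; a first post-dose sample, if wanted, should be listed and labelled separately.

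The cost is wording in the protocol, CRF and SAP, a few minutes of staff and patient time for up to four requested voids, and at most one extra sodium assay per patient. No visit or observation time is added. Some patients may not void on request, but Section 4.2 already excludes "Presence or need for urinary catheterization, urinary tract abnormality or disorder interfering with urination".
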